12.2 Statistical analysis

All major treatment comparisons between the two randomized groups in this trial will be performed according to the principle of "intention-to-treat", that is, subjects

CA163-157 Clinical Protocol

will be analyzed according to the treatment arm to which patients were randomized, regardless of compliance to assigned treatment. Summary statistics will be provided for overall response rates and pCR rates by treatment arm. The different rates between treatment arms will be compared by Cochran-Mantel-Haenszel test. . Logistic regression models will be used to assess the association between expression of biomarkers (such as PTEN, EGFR and EGFR-pathway associated genes (including, but not limited to TGF- α , CRYAB, NRAS, KRAS, AKT3, PTEN, MEK1 and KRAS amplicon genes) from the baseline and the overall objective or pathologic response, controlled by treatment arm, age, and disease stage. The unpaired t-test will be applied to compare the difference of expression of biomarkers between the baseline and at surgery in the two arms. Benjamini and Hochberg adjustment will be used to adjust multiple comparisons in expressions of all marks. Safety and toxicity of each regimen will be tabulated by type and grade at the end of chemotherapy. Radiographic efficacy assessment will be performed on all patients at the end of chemotherapy. Statistical significance is defined as 2-tailed p=0.05 level. Stata Version 10 (College Station, TX) will be used for all statistical analyses.

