2.2 Screening/Baseline visit

Informed consent must be obtained before performing any study-related procedures. Screening procedures may be done up to 4 weeks prior the start of neo-adjuvant therapy. Screening evaluation will include blood work, pregnancy testing, medical history, physical exam (including tumor measurements of the breast and lymph node, height, weight, blood pressure, heart rate and temperature) electrocardiogram, and echocardiogram. Tumor measurements will be recorded as the largest dimension in centimeters. Medical history should include relevant underlying conditions and concomitant medications. Baseline signs and symptoms are to be recorded and followed throughout the trial. A mammography and ultrasound will be performed to assess disease status. Prior to initiation of neo-adjuvant therapy, a core tumor breast biopsy and blood sample will be obtained for baseline biomarkers expression studies. If a patient entered the study (i.e. signed informed consent) prior to histological confirmation of breast cancer, this biopsy may serve the dual purpose of confirming the diagnosis and obtaining tissue for biomarkers research. Following confirmation of eligibility, a blocked randomization will be used to randomize patients to either arm 1 or arm 2. A master sequence of randomization numbers for each arm will be generated.

For those study patients who voluntarily agree to have an optional serum samples taken for biomarkers expression; blood samples will be stored and the biomarkers expression will be done at later time (see lab manual). Patients will be informed that they will not be excluded from the clinical study if they do not wish to participate in the (blood samples) biomarkers study. •The biomarkers blood sample must be collected after a patient number has been obtained. (see CA163157 Procedure Manual).

• A minimum of 15 tissue slides from the tumor breast biopsy or lymph nodes (when available) will be collected at baseline and send to the central laboratory. Note: please collect all tissue slides (15 at baseline and 15 after surgery) at the site before send it out to the central lab (see lab manual)

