given in a dose of 40 mg/m² as a 3-hour IV infusion every 3 weeks. A total of 161 subjects were treated. Median age was 55 years. Results in evaluable subjects were Primary Best Overall Response Rate (Complete Response [CR] or Partial Response [PR]): 98/161 (61%); Pathologic Complete Response in Breast [pCR_B]: 29/161 (18%); and Pathologic Complete Response in Breast and Lymph Nodes [pCR_{BL}]: 17/161 (11%). Independent assessment of subject responses yielded pCR_B and pCR_{BL} rates of 14% and 9%, respectively. In subjects with ER-negative, ER-/PR-negative, and triple-negative tumors, as assessed by locally read immunohistochemistry (IHC) and fluorescence in situ hybridization (FISH), investigator-assessed pCR_B rates were 29%, 33%, and 26%, respectively. The pCR_{BL} rates were 19%, 23%, and 19%, respectively.

No deaths were reported. Twelve (8%) subjects reported SAEs. Among these subjects, 10 (6%) reported at least 1 SAE assessed as possibly, probably, or certainly related to ixabepilone therapy. These SAEs included peripheral or sensory neuropathy, febrile neutropenia, neutropenia, vomiting, and hypersensitivity, each reported in 2 subjects; and mucositis, constipation, diarrhea, stomatitis, lymphopenia, leukopenia, thrombocytopenia, increased ALT, and increased AST, each reported in 1 subject.

Treatment-related adverse events were reported in 97% of subjects. The most common (\geq 15% of subjects) were alopecia (86%), myalgia (50%), arthralgia (30%), asthenia (27%), neutropenia (21%), peripheral sensory neuropathy (20%), nausea (19%), fatigue (19%), and diarrhea (15%). Most were Grade 1 to 2. Grade 3/4 treatment-related adverse events were reported in 25% of subjects. The most common Grade 3/4 event was neutropenia (14%).¹²

CA163-081: Phase 2 Study in Refractory MBC

CA163-081 was a single-arm, open-label, multicenter, multinational, two-stage design study of ixabepilone in MBC that was resistant to an anthracycline, a taxane, and capecitabine. A total of 126 subjects were treated. Data from this study have been published. Of the 126 treated subjects, 113 were evaluable for response. Subjects were heavily pretreated: 88% had received \geq 2 lines of prior chemotherapy in the metastatic setting. Independent Radiology Facility (IRF)-

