7.0 Treatment Plan/Methods

This is a randomized open-label phase II trial; 116 triple negative breast cancer patients will be randomized equally between 1) Ixabepilone or 2) Ixabepilone plus Cetuximab. The study population will include patients≥ 18 years of age diagnosed with invasive mammary carcinoma. Patients will be assigned to treatment arms using a stratified blocked randomization, with strata based on disease stage (T1N1-3M0 or T2-4 N0-3M0). All patients will receive a physical assessment, imaging, a blood draw, and a core needle biopsy (CNB) a biopsy prior to the start of treatment.

7.1 Treatment Arm 1

Patients will receive Ixabepilone 40mg/m² given over approximately 3-hours on day 1 Patients will receive a total of four cycles of this combination with each cycle given 21(+/- 3) days.

Subjects will be premedicated approximately 1 hour before the ixabepilone infusion with either 1) both an oral H1 blocker (diphenhydramine 50 mg or equivalent) and an oral H2 blocker (e.g., ranitidine 150 300 mg or cimetidine 300–800 mg or nizatidine 150-300 mg or famotidine 20–40 mg); or 2) with premedication per institutional standards. Premedication with steroids is indicated in subjects who developed a hypersensitivity reaction to ixabepilone in previous cycles. Patients with severe reaction should not be retreated (see dose modification chart below).

7.2 Treatment Arm 2

Patients will receive Ixabepilone 40mg/m^2 given over approximately 3-hours on day 1 followed by Cetuximab given on day 1 at 400 mg/m² as an initial loading dose (first infusion) administered as a 120-minute IV infusion (maximum infusion rate 5 mL/min) followed by 250 mg/m² infused over 60 minutes (maximum infusion rate 5 mL/min) as a subsequent weekly dose. Patients will receive a total of 4 cycles of this combination with each cycle being 21 (+/-3) days.

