8.0 CRITERIA FOR RESPONSE

8.0.1 PATHOLOGICAL RESPONSE: The histologic response after treatment will be evaluated in the primary tumor and in the axillary lymph nodes removed by axillary dissection. In the primary tumor, cellular modifications will be evaluated in both the infiltrating tumoral component and in the possible ductal component, if applicable:

- Analysis of the viable residual infiltrating component (% of total tumoral mass)

- Analysis of the residual ductal component (% of total tumoral mass)
- Determination of the mitotic index.

In the axillary lymph nodes: analysis of the viable residual component. The criteria of pathological response will be defined according to the Sataloff Classification ⁴⁶.

The response in the primary tumor site will be graded from A to D.

Primary site response:

T-A Total or near total therapeutic effect.

T-B Subjectively greater than 50% therapeutic effect but less than total or near total.

T-C Less than 50% therapeutic effect, but effect evident

T-D No therapeutic effect.

Axillary lymph node response:

N-A Evidence of therapeutic effect, no metastatic disease.

N-B No nodal metastasis or therapeutic effect.

N-C Evidence of therapeutic effect but nodal metastasis still

Present.

N-D Viable metastatic disease, no therapeutic effect

pCR corresponds to pathological grades T-A; N-A, N-B.

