12.1 Sample size estimate

The published study CA163-080 has shown that the pathological complete response (pCR) rate is 18% based on a single agent Ixabepilone data, and is the same percentage that we assume for patients that will be treated with ixabepilone (Treatment Arm 1). With total 108 patients (54 in each arm), we will be able to detect 25% difference in pCR rates between the arm with Ixabelpilone plus Cetuximab (Treatment Arm 2) and Arm 1 with 81.9% power and a two-sided significance level of 0.05. A total of 116 patients will be enrolled to allow for 6.5% dropout before randomization of 108 patients. Table 1 provides power estimates to detect hypothesized 25%, 27%, 29%, and 31% difference in pCR rate in the treatment am 1 compared to the treatment arm 2 with given sample size of 54 patients in each arm.

Projected pathological complete response rate		Estimated power (%)
Treatment Arm 1	Treatment Arm 2	
18%	0.43%	81.9
	0.45%	87.0
	0.47%	91.0
	0.49%	94.0

Table 1. Power to detect different differences of pathological complete response rates in the two arms with given sample size of 54 patients in each arm.

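### Section 12.2 names no strata for the primary CMH test; baseline strata that separate N0 from N1-3 within T2-4 would be a low-cost improvement, not the correction of an error

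*Combined protocol and SAP*

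**What the plan says.** - **Primary test (12.2):** "The different rates between treatment arms will be compared by Cochran-Mantel-Haenszel test". No stratification variable is given. Disease stage appears in 12.2 only as a covariate in the biomarker logistic models, and no analysis names nodal status.
- **Stage factor (7.0):** patients are randomised in blocks "with strata based on disease stage (T1N1-3M0 or T2-4 N0-3M0"). The study summary and the synopsis give the same factor. Section 6.3 mentions blocking only.
- **Endpoint (8.0.1):** pCR is grade T-A in the breast together with N-A or N-B in the axilla. The second axillary grade reads "N-B No nodal metastasis or therapeutic effect".
- **Baseline data:** N category is part of eligibility (6.1). Screening includes a "physical exam (including tumor measurements of the breast and lymph node"), and 2.2.1 adds ultrasound of the nodal region.
- **Prior data (4.0.2, CA163-080):** for ER-negative, ER-/PR-negative and triple-negative tumours, investigator-assessed breast pCR "rates were 29%, 33%, and 26%, respectively". The breast-and-node rate for triple-negative tumours was 19%.
- **Power (12.1):** "With total 108 patients (54 in each arm") and "81.9% power and a two-sided significance level of 0.05", for 18% versus 43%.

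**The concern.** A Cochran-Mantel-Haenszel test is defined by its strata, so 12.2 leaves the primary analysis open between an unstratified test, one stratified by stage, and something else. The natural candidate is the randomisation factor, but it does not line up with the endpoint. Its first level is entirely node-positive. Its second level, which takes every T2-4 patient, mixes two groups. Those with uninvolved nodes need only a breast response, because N-B satisfies the axillary half. Those with involved nodes must clear both sites. The endpoint definition therefore makes baseline nodal status a plausible predictor of pCR.

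What is at stake is precision. If the arms differ by chance in the share of node-positive T2-4 patients, neither an unstratified nor a stage-only test adjusts the pCR comparison for it, although the information was recorded before treatment.

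**Working it through.** **1. The plan's own figure.** Inputs from 12.1: 54 per arm, 18% versus 43%, two-sided 0.05. Exact enumeration of the uncorrected Pearson chi-square gives 81.9%, as stated; the pooled normal approximation gives 81.5%. The present point leaves this figure untouched.

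**2. Implied pCR by nodal status.** The documents do not give it. Assume that breast pCR is 26% whatever the nodal status and that N0 patients need only the breast response. With f the node-positive share, the triple-negative CA163-080 rates give

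0.19 = 0.26(1 - f) + r f, so r = [0.19 - 0.26(1 - f)] / f.

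- f = 0.40: r = (0.19 - 0.156)/0.40 = 8.5%; odds ratio N0:N+ about 3.8
- f = 0.50: r = (0.19 - 0.13)/0.50 = 12%; odds ratio about 2.6
- f = 0.70: r = (0.19 - 0.078)/0.70 = 16%; odds ratio about 1.8

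**3. Size of chance imbalance.** With no control of nodal status, the SD of the between-arm difference in node-positive share is sqrt[2f(1 - f)/54]. At f = 0.5 it is 0.096, so the 95% range is about ±1.96 × 0.096 = ±19 points. At f = 0.5 the N0-N+ gap in pCR is 26 - 12 = 14 points, so such an imbalance moves the observed pCR difference by 0.189 × 0.14 = 2.6 points. Gaps of 10 to 20 points give about 2 to 4 points, against a 25-point target.

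**4. Power by simulation.** There were 60,000 trials per scenario, with 54 per arm and 10% T1N+ balanced by the randomisation. Nodal status was left to chance within T2-4. Overall pCR was 19% versus 44%, with a constant treatment odds ratio. The 19% is the triple-negative breast-and-node rate, and the plan's 25-point gap is kept. Each cell shows power with stage-only strata / with the three nodal strata.

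| Node-positive share | All trials | Arm 2 has at least 10 points more N+ |
|---|---|---|
| 40% | 81.7% / 83.7% | 68.8% / 82.4% |
| 55% | 81.3% / 82.3% | 72.6% / 81.1% |
| 70% | 81.2% / 81.4% | 74.5% / 80.4% |

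- Average gain: 2.0, 1.0 and 0.2 points.
- An imbalance of at least 10 points in either direction occurs in 24-27% of trials, so against Arm 2 in about 12-13%.
- In the mirror case, with the excess of node-positive patients in Arm 1, stage-only power is about 87-91% and nodal-strata power about 81-83%. Repeat runs of these conditional figures agree to within about a point.
- Without a treatment effect, rejection is about 5% with either analysis.

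**5. Other nodal effects, at the plan's 18% versus 43%.** There were 40,000 trials per scenario, with 40-60% of T2-4 patients node-positive and simple 1:1 randomisation.

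| Odds ratio N0:N+ | Stage only | Stage plus nodal status |
|---|---|---|
| 1 | 81.6% | 81.3% |
| 2 | 81.8% | 82.2% |
| 3 | 81.8% | 83.3% |
| 5 | 81.9% | 85.6% |

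An unstratified test performs like the stage-only test throughout (81.5-82.1%). Type I error is 4.7-5.2% across all the versions.

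**6. Inaccurate nodal staging.** With an assumed 20% misclassification in each direction, the averages in step 4 become 81.8/82.1%, 81.3/81.5% and 81.5/81.3%. The protection against an adverse imbalance shrinks to about 2-4 points.

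**The case against.** The strongest case against acting is that nothing here is wrong. Randomisation protects the test whether or not a prognostic covariate is used, and analysing by the randomisation factor would be conventional. The average gain is at most about 2 points under the main assumptions. It nearly vanishes if clinical staging is imprecise, which is plausible: the baseline axilla is assessed by examination and ultrasound with no nodal biopsy required for staging, whereas N-A and N-B are read on the surgical specimen. Age or T category could be proposed on similar grounds. All of this stands, except that nodal status has a link to pCR through the endpoint definition itself, which the other two lack.

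A reader might also infer more than the documents support:

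- **That the primary test is biased or invalid.** It is not; its type I error is about 5%.
- **That the plan prescribes a CMH test stratified by stage.** Section 12.2 names no strata. Stage-only is a plausible reading, not a stated one.
- **That nodal status is wholly ignored.** The T1 stratum is entirely node-positive; the mixing is confined to T2-4.
- **That there is a one-in-four chance of losing 6-14 points of power.** The 24-27% covers both directions. Half of those trials favour Arm 2, and there the test without nodal strata rejects more often.
- **That CA163-080 measures the nodal effect.** A breast-and-node response is a subset of breast responses, so a fall from 26% to 19% is in the expected direction by construction. It does not give pCR in N0 and N+ patients separately.

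**Conclusion.** The point holds as a recommendation to specify and refine the analysis. Two facts come straight from the documents: the CMH strata are not named, and the only stage factor pools T2-4 patients with and without a nodal hurdle for pCR. The size depends on the assumed nodal effect, node-positive share and staging accuracy, none of which the documents supply. Within the assumed range the average benefit is small. The more useful gain is stability: nodal strata hold power at roughly 80-83% whichever way the nodes fall, where a test without them ranges from about 69% to 91%. The sample size and the stated 81.9% power need no change.

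**What to change.** In 12.2, name the primary CMH strata for pCR as T1N1-3, T2-4N0 and T2-4N1-3, taken from baseline staging, and report the matching stratified risk difference with its 95% CI. These levels nest inside the randomisation strata. Under the 10% assumption T1N1-3 would hold only about 11 of 108 patients, which a CMH test tolerates. Align 6.3 with 7.0 so that both say the blocks are stratified by stage.

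Fix the wording before outcomes are compared by arm. The trial is open-label, and an adjustment chosen after an imbalance is visible would be open to challenge.

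The cost is wording only, since the staging data are already collected. The downside is about 0.3 points of power if nodal status turns out not to be prognostic.

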Ixabepilone BMS-247550 CA163-157 Clinical Protocol

TMHRI IRB#0908-0265 BMS Protocol #: CA163-157

ICE Trial

RANDOMIZED OPEN-LABEL NEO-ADJUVANT PHASE II STUDY COMPARING IXABEPILONE (I) VS IXABEPILONE PLUS CETUXIMAB (IC) IN TRIPLE NEGATIVE BREAST CANCER PATIENTS (ICE)

VERSION: 8.0 DATE: 8/9/2012 PHASE: II IND Number: 104,307

[name]. Director, Methodist Cancer Center The Methodist Hospital/Weill Cornell University [name] [contact] [contact] [contact]

STUDY SUMMARY

Title:	Randomized open-label neo-adjuvant phase II study comparing					
	ixabepilone (I) vs. ixabepilone plus cetuximab (IC) in Triple negative breast					
	cancer patients					
Objectives:	Primary Objective:					
	1. To determine the pathologic complete response rate (pCR) (breast and					
	axilla) of Ixabepilone versus Ixabepilone when combined with cetuximab					
	in patients with invasive breast adenocarcinoma T1N1-N3M0 or					
	T2-4 N0-3M0 disease who are Triple negative and who are candidates for					
	preoperative chemotherapy.					
	Secondary Objective(s):					
	1. To evaluate overall objective response rate in both treatment groups.					
	2. To assess toxicity of each regimen.					
	Exploratory Objectives:					
	1. To correlate the expression of biomarkers such as PTEN, EGFR					
	and EGFR-pathway associated genes (including, but not limited to,					
	TGF- α , CRYAB, NRAS, KRAS, AKT3, PTEN, MEK1 and KRAS					
	amplicon genes) with the objective clinical and pathologic response.					
	2. To potentially explore other gene/protein expression patterns,					
	mutations and gene/chromosomal copy number alterations related					
	to sensitivity or resistance to ixabepilone, other anti-microtubule					
	agents and cetuximab. These additional exploratory analyses may					
	include, but are not limited to, beta tubulin isoforms, ABC					
	transporters, TACC3, HCAPG, GTSE1, Kallikreins and defined					
	gene models associated with ixabepilone response.					

Study	-Patients with either T1N1-N3M0 or T2-4 N0-3M0 disease who are Trip				
population:	on: negative and who are candidates for preoperative chemotherapy.				
Sample	116 patients.				
Size:					
Number of	Single Institution: The Methodist Hospital Research Institute.				
Centers:					
Treatment	This is a randomized open-label phase II trial; 116 triple negative breast				
Plan:	cancer patients will be randomized equally between 1) Ixabepilone or				
	2) Ixabepilone plus Cetuximab.				

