- Additional exploratory biomarker analysis may be performed on tumor or blood samples during or following the study. Such exploratory analyses may include assessments of somatic gene mutation, gene/chromosome copy number alteration and gene/protein expression for genes/proteins related to sensitivity or resistance to ixabepilone, other micro-tubule agents and cetuximab. These exploratory biomarkers may include, but are not limited to, beta tubulin isoforms, ABC transporters, TACC3, HCAPG, GTSE1, Kallikreins and gene models associated with ixabepilone response.

These analyses will allow for the correlation of biomarkers expression and response to treatment. Tumor tissue samples will be obtained from the original paraffin blocks or slides containing tumor tissue from the initial diagnostic work-up (see section 7.1).

In addition to the diagnostic core needle biopsy for biomarkers at baseline a second search for the same biomarkers will be done at the time of surgery. The following tests will be conducted (prioritized in the order below):

- EGFR expression by IHC
- PTEN expression by IHC
- Estrogen receptor expression by IHC (at baseline only)

- Progesterone receptor expression by IHC (at baseline only)
- Her2 neu expression by IHC and/or FISH (at baseline only)
- Ki67 (MIB-1) by IHC (at baseline only)
- TGF- α expression by mRNA-based assay
- CRYAB expression by mRNA-based assay
- NRAS expression by mRNA-based assay
- KRAS expression by mRNA-based assay
- AKT3 expression by mRNA-based assay
- MEK1 expression by mRNA-based assay
- KRAS amplicon genes expression by mRNA-based assay
- Beta tubulin isoforms
- ABC transporters
- TACC3
- HCAPG
- GTSE1
- Kallikreins and defined gene models associated with ixabepilone response.
- Additional exploratory biomarkers related to ixabepilone, anti-microtubule and cetuximab sensitivity or resistance

The goal of this clinical research study is to compare the effectiveness of each study group of chemotherapy in triple negative breast cancer patients, and to evaluate the pathologic response rate for each group. We will be collecting tissue from the primary tumor for biomarker testing; the procedure will be done at baseline, and at the time of surgery.

TMHRI Version: 8

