were HER2 positive, 58% were TNeg. 79% had prior chemotherapy for MBC. Pts received a median of 2 cycles (range: 1-11) of treatment. Confirmed RR was 11% (95% CI: 1-33%), with 1 PR and 1 CR. One pt had stable disease for 11 cycles. RR and clinical benefit rate (CBR: RR + stable > 6 months) for Tneg vs non- Tneg was 18% vs 0% (p=0.49) and 27% vs 0% (p=0.23). 12 pts progressed on therapy within 2 cycles. With low response rate and rapid progression, the study closed early. NCI CTC version 3 grade 3-4 adverse events occurred in 10 pts; only dermatologic toxicity (derm tox) had a > 5% incidence (26%). Patients with grade > 2 derm tox had a CBR of 21% (3/14) vs 0% in patients with grade 0-1. 18 pts have progressed with a median time to progression of 1.4 mos (95% CI: 1.1-2.2 mos). 15 pts have died with a median overall survival of 9.4 mos (95% CI: 3.3-16.1 mos). UGT1A1 results will be presented. Conclusions: Irinotecan and cetuximab has minimal activity in this population. Tolerability is acceptable. There was a numerically higher CBR in Tneg pts and patients with grade > 2 derm tox, but small pt numbers limit conclusions. Better predictive factors for response to EGFR inhibition are needed. NCI CA-25224, CA-63848, CA-37404, CA- 60276, Bristol-Myers Squibb, Imclone systems²².

Preliminary results of a randomized phase II study of weekly Irinotecan /carboplatin with or without cetuximab in patients with metastatic breast cancer. O'Shaughnessy and colleagues also presented data on the use of cetuximab in a randomized phase 2 study of weekly irinotecan (90 mg/m²) and carboplatin (AUC 2), with or without cetuximab (250 mg/m²). In the overall intention-to-treat study population, response rate improved marginally from 28% to 33% with the addition of cetuximab. Approximately half of the study population (78 patients) had triple-negative tumors. In that subgroup, cetuximab was associated with a response rate of 49% compared with 30% when chemotherapy was used alone. No significant differences in PFS or overall survival were observed in any subgroup, and significant toxicity led to dose reductions in starting doses of the chemotherapy agents. Based on the available evidence, there is little reason to believe that either single-agent cetuximab or a small molecule tyrosine kinase inhibitor of EGFR will have substantial activity in the triple-negative setting. It remains unknown whether these agents will prove useful in this context when combined with chemotherapy²³

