4.0. 4. Biomarkers Rationale Assessments:

EGFR

Epidermal growth factor receptors (EGFRs) are the prototypic members of a family of growth factors derived from membrane-anchored precursors. All members of this family are characterized by the presence of at least one EGFR structural unit in their extracellular domain. Increased expression and activation of receptor tyrosine kinases occurs frequently in human breast carcinomas.

Roughly 35% breast cancers express EGFR as ascertained by IHC and its expressed with a 2-fold higher frequency in hormone receptor negative breast cancers compared to hormone receptor positive breast cancers .^{24,25,26}

A wide variety of *in vitro* and *in vivo* biological effects have been ascribed to EGF and other members of the EGF family. EGF promotes proliferation and differentiation of mesenchymal and epithelial cells. EGF family ligand-receptor signaling is implicated in a wide variety of human carcinomas. Several therapies targeting these receptors are currently in clinical trials and therapeutic strategies including blockage of individual receptors with monoclonal antibodies and inhibition of tyrosine kinase function. ^{27, 28, 29} Insufficient data exists to suggest a link between EGFR protein expression and response to EGFR inhibitors in breast cancer. ³⁰

PTEN

PTEN is a tumor suppressor that negatively regulates the PI3 kinase pathway, which is downstream of EGFR. Loss of PTEN protein expression, attributed to loss of heterozygosity and/or post-transcriptional modification, is exhibited in 16 - 37% of breast cancers^{31, 32}. PTEN-loss is significantly associated with HR-

Ixabepilone BMS-247550

negative breast cancers. ^{33, 34, 35} Studies has been shown to confer resistance to EGFR inhibitors *in vitro* in breast cancer cells and to predict response to Erbitux in metastatic colorectal cancers ^{36, 37, 38}.

EGFR-associated signature genes

Hoadley et al showed that the expression of a number of EGFR-pathway related genes are associated with the basal-like subtype, including: TGF- α , CRYAB, NRAS, KRAS, AKT3, PTEN, MEK1 and KRAS amplicon genes. In addition, this group identified three gene signatures that correlated with EGFR activity in vitro that could be identified in two breast cancer patient cohorts. While the genes in these signatures do not appear to be directly related to the EGFR pathway, they may still have predictive value.³⁹

Other exploratory biomarkers

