Additional exploratory biomarkers related to ixabepilone, anti-microtubule and cetuximab sensitivity and resistance may be assessed. Markers shown to have an association with paclitaxel resistance, include beta tubulin isoforms, specifically beta III tubulin ⁴⁰ and ABC transporter expression, specifically MDR1 and MRP7⁴¹. The capacity of these biomarkers to predict response to ixabepilone has not been established, as yet. Preliminary analyses have suggested that several gene models, including TACC3, HCAPG, GTSE1, Kallikreins and pre-defined gene sets, may be able to differentiate ixabepilone activity from paclitaxel activity. These models were derived from a comparison of gene expression patterns of pathological CR patients in microarray data available from two neoadjuvant breast cancer studies, CA163-080 (ixabepilone monotherapy) and MDA-133 (paclitaxel-FAC combination therapy) ⁴².

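### The biomarker-response model has no biomarker-by-arm term, so it can flag a marker but cannot attribute the association to cetuximab

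*Combined protocol and SAP*

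**What the plan says.** The only analysis linking markers to response is in section 12.2: "Logistic regression models will be used to assess the association between expression of biomarkers", measured at baseline, and "the overall objective or pathologic response, controlled by treatment arm, age, and disease stage". Neither that section nor any other specifies a biomarker-by-arm product term, a separate fit in each arm, or a treatment effect by marker level. The other biomarker test in 12.2 is an unpaired t-test on expression at baseline and surgery, and response plays no part in it. A Benjamini-Hochberg adjustment follows that t-test and is worded in terms of marker expression.

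There are two exploratory objectives. The first asks for the correlation of markers with clinical and pathologic response. The second is optional. In the Study Summary it begins "To potentially explore other gene/protein expression patterns", and section 1.3 allows further work on "genes/proteins related to sensitivity or resistance to ixabepilone, other micro-tubule agents and cetuximab".

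The background makes the agent part of the question. Section 4.0.3 reports the conclusion of a cetuximab trial: "Better predictive factors for response to EGFR inhibition are needed". Section 4.0.4 says of EGFR: "Insufficient data exists to suggest a link between EGFR protein expression and response to EGFR inhibitors in breast cancer". It says that PTEN loss makes EGFR inhibitors less effective "in breast cancer cells and to predict response to Erbitux in metastatic colorectal cancers". On the tubulin and transporter markers it says: "The capacity of these biomarkers to predict response to ixabepilone has not been established, as yet".

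**The concern.** Both arms receive ixabepilone; they differ only in cetuximab. A marker of general chemosensitivity, or of ixabepilone sensitivity, should relate to response in both arms. A marker of cetuximab sensitivity should relate to response more strongly, or only, in arm 2. What separates the two is the difference in marker effect between the arms. The planned model sets that difference to zero and estimates one odds ratio per marker.

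The trial could therefore report that a marker is associated with pCR without being able to say whether cetuximab has anything to do with it. A marker whose effect changes direction between arms could also go unseen. The randomised ixabepilone-only arm is the comparison needed, and the plan does not use it for this.

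**Working it through.** **Inputs from the plan.** Section 12.1: 54 patients per arm, pCR 18% in arm 1 and 43% in arm 2, two-sided 0.05, 81.9% power. The documents give no figure for the biomarker model.

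**The plan's own figure.** With the pooled-variance normal approximation,

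power = Φ{[0.25 − 1.96·√(2·0.305·0.695/54)] / √[(0.18·0.82 + 0.43·0.57)/54]} = Φ{(0.25 − 0.1737)/0.0853} = Φ(0.895) = 81.5%.

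This agrees with the stated 81.9% to within half a point. Enrolment is 108/(1 − 0.065) = 115.5, rounded up to 116, as stated.

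**Assumptions.** The documents do not give marker prevalence or pCR by marker status. I assume a binary marker, keep mean pCR at 18% and 43%, and leave out age and stage.

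**Can the planned model tell the markers apart?** At 50% prevalence there are 27 patients per cell. A logistic model with only arm and marker main effects uses the responses only through the arm totals and the marker totals. Two markers with the same totals give the same fit.

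| Assumed marker | Arm 1 pCR, −/+ | Arm 2 pCR, −/+ | Odds ratio, arm 1 / arm 2 | Mean pCR, − / + | Pooled odds ratio |
|---|---|---|---|---|---|
| Acts only with cetuximab | 18% / 18% | 25% / 61% | 1.0 / 4.69 | 21.5% / 39.5% | 2.57 |
| Same odds ratio in both arms | 11.3% / 24.7% | 31.7% / 54.3% | 2.57 / 2.57 | 21.5% / 39.5% | 2.57 |
| Opposite effects | 26% / 10% | 35% / 51% | 0.32 / 1.93 | 30.5% / 30.5% | 1.00 |

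For example, the arm 2 odds ratio in the first row is (0.61/0.39)/(0.25/0.75) = 4.69. The first two rows share every total, so the planned fit is identical: marker odds ratio 2.57, arm odds ratio 3.63. In 2,000 simulated trials of each, the planned marker term was significant in 57% and 56%. An added interaction term was significant in 40% and 6%.

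**What the interaction term can deliver.** With L the log ratio of the arm-specific odds ratios, n = 54, q the share of the arm in each marker group and p the cell pCR,

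SE² = Σ 1/[n·q·p(1 − p)] over the four cells; power ≈ Φ(|L|/SE − 1.96); 95% interval factor = exp(1.96·SE).

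For the first row, SE² = 2/(27·0.18·0.82) + 1/(27·0.25·0.75) + 1/(27·0.61·0.39) = 0.502 + 0.198 + 0.156 = 0.855, so SE = 0.925. L = ln 4.69 = 1.546. Power = Φ(1.67 − 1.96) = 39%, and the interval factor is 6.1.

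The range below keeps arm 1 flat at 18%, with prevalence 20-70% and a marker contrast of 20-50 points in arm 2, limited to cases where marker-negative arm 2 patients do no worse than 18%.

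- Unadjusted interaction power is roughly 11-66% (14-65% by likelihood-ratio simulation, whose true size of 5.8-6.5% flatters it slightly).
- If the whole gain falls in marker-positive patients, power is about 74% at prevalence 0.45, 83% at 0.40 and 89-94% at 0.35.
- With 80% of tissue available (43 per arm), simulated power is 13-56%.
- At 0.05/8, the strictest Benjamini-Hochberg step for eight markers, simulated power with 54 per arm is 3-37%.
- The interval factor is 5.9-6.6 at 50% prevalence and 9.1-11.4 at 20%.

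**The case against.** The strongest reply is that the model is being held to an aim it was not written for. The markers named in the logistic sentence are those of the first objective, which asks only for correlation, and the model does that properly. The second objective is optional, may be pursued after the study, and has no method prescribed or ruled out. This stands, and it limits the point to an improvement. It does not remove it: the marker list is open-ended, and no other marker-response analysis is given for the second objective.

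A reader might infer that the planned model cannot address the second objective at all. That goes too far. The pooled model can flag a cetuximab-only marker, and for markers acting in the same direction it does so with more power than the interaction test. At 50% prevalence and arm 2 contrasts of 20, 26, 36, 46 and 50 points, approximate power is 21, 33, 55, 75 and 81% for the marker term against 15, 22, 39, 58 and 66% for the interaction. What the model lacks is attribution. The opposite-effects case shows what can happen, but nothing in the documents suggests that any listed marker behaves that way.

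It is also fair that the added test is weak. That calls for cautious reporting. It does not make the pooled odds ratio answer the attribution question, because that limit lies in the form of the model and would remain at any sample size.

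**Conclusion.** The point holds as a low-cost improvement to an exploratory analysis. The planned model suits the first objective and is a sensible overall screen. For the cetuximab part of the second objective it cannot separate a marker acting only with cetuximab from one with a common effect: both give a pooled odds ratio of 2.6 in the illustration, where the arm-specific values are 1.0 and 4.7 in one case and 2.6 and 2.6 in the other.

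The structural conclusion needs no assumption beyond the model as written. The sizes rest on assumed marker splits and prevalence, a binary marker (many listed assays measure mRNA expression), and no age or stage terms.

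A reader might take this to weaken the trial's main result. The documents do not support that: the primary pCR comparison, sample size, stated power and safety assessment do not use this model.

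**What to change.** Keep the planned logistic model as the overall screen. Add to section 12.2 that, for each marker, a second model will include a biomarker-by-arm term; that arm-specific odds ratios will be reported with 95% confidence intervals; that the Benjamini-Hochberg adjustment will also apply to the interaction p-values; and that these results are exploratory. The adjustment needs saying because the current sentence does not clearly cover the response models.

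The cost is a sentence or two in the plan and a few lines of code, with no new data or patients. The downside is precision. Among the scenarios examined, unadjusted power exceeds about 70% only if the whole cetuximab gain falls in about 45% of patients or fewer, and it drops with multiplicity adjustment or missing tissue. The interval for the ratio of odds ratios runs a factor of about 6-7 either way at 50% prevalence and 9-11 at 20%. The plan should therefore say that a non-significant interaction does not show a marker to be unrelated to cetuximab.
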